#### Table 9-2. Dose modifications for mocetinostat

Mocetinostat dose levels and reductions*	
Starting dose 0	70 mg three times per week
Dose level 0	70 mg three times per week
Dose level –1	50 mg three times per week
Dose level –2	35 mg three times per week**

\*Dose reduction should be based on the worst preceding toxicity

\*\*Dose reduction below 35 mg 3x/week is not allowed. If a dose reduction below 35 mg 3x/week is required, the patient should be permanently discontinued from mocetinostat.

#### 9.3. Guidelines for dose reduction based on toxicities

#### 9.3.1. Management on non-hematologic toxicities

In the case of drug-associated grade 3 non-hematologic toxicities experienced by the subject, hold treatment (one or both drugs if applicable) until toxicity is resolved to  $\leq$  grade 1 or to baseline value. If further treatment is desired, treatment should then be resumed at the next lower dose level for the applicable drug(s). If the toxicity can be managed by routine supportive care, such as anti-emetics or electrolyte supplementation, then a dose reduction is not required. If there is no recovery within 21 day the subject will go off protocol treatment, unless the clinical investigator in discussion with MethylGene/Mirati deems that it is in the best interest of the subject to resume treatment. If grade 3 non-hematologic toxicity recurs following the first dose reduction, a second dose reduction of one dose level may be implemented following recovery to  $\leq$  grade 1 or to baseline. However if grade 3 non-hematologic toxicity again recurs, then the subject should be removed from protocol therapy. Subjects who experience grade 4 non-hematologic toxicities should have study treatment discontinued, unless the Investigator and the sponsor agree that the subject is benefiting from study treatment, in which case, treatment may be resumed at a lower dose level as described above following recovery. Dose reductions for lower-grade toxicities may also be implemented based on Investigator discretion; however the sponsor should be notified of such an event (Table 9-3).

Table 9-3. Dose Modifications – Non-Hematologic Drug Related Toxicities 					
Occurrence	Toxicity	Treatment Delay	Dose Modification		
1st Occurrence	< Grade 3	May be implemented based on Investigator and subject			
		discretion; Sponsor should be no	otified		
	Grade 3	Hold until ≤ Grade 1 or return	Then, resume at next lower		
		to baseline	dose level		
	Grade 3 toxicity manageable	Hold until ≤ Grade 1 or return	Not required		
	with routine supportive care	to baseline			
	Grade 4		Remove from Therapy		
2nd Occurrence	Grade 3	Hold until ≤ Grade 1 or return	Then, resume at next lower		
		to baseline	dose level (e.g., 2nd dose		
			reduction)		
3rd Occurrence	Grade 3		Remove from Therapy 		

1For pericardial toxicity, see Section 6.2.2.

2 Unless the Investigator and the sponsor agree that the subject is benefiting from study treatment, in which case, treatment may be resumed at the next lower dose level as described above following recovery.

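### Section 9.3.1 text and Table 9-3 give different rules for repeated grade 3 non-hematologic toxicity: how far the supportive-care waiver reaches, and what counts toward removal

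*Combined protocol and SAP*

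**What the plan says.** Section 9.3.1 of the combined protocol and SAP gives the rules twice, as a paragraph and as Table 9-3, which the paragraph cites.

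- **Text, waiver.** The default is to hold treatment until recovery and resume one dose level lower. The exception follows: "If the toxicity can be managed by routine supportive care, such as anti-emetics or electrolyte supplementation, then a dose reduction is not required". No occurrence number is attached.
- **Text, later steps.** "If grade 3 non-hematologic toxicity recurs following the first dose reduction, a second dose reduction of one dose level may be implemented", once the patient has recovered. Then: "However if grade 3 non-hematologic toxicity again recurs, then the subject should be removed from protocol therapy".
- **Table 9-3, first occurrence.** The supportive-care row ("Grade 3 toxicity manageable" by routine supportive care) appears only in this block, with no dose modification required.
- **Table 9-3, second occurrence.** The row names grade 3 alone and sends the patient to the next lower level, with a parenthetical example that begins "dose level (e.g., 2nd dose".
- **Table 9-3, third occurrence.** Removal, qualified by footnote 2, which reads in part: "Unless the Investigator and the sponsor agree that the subject is benefiting from study treatment, in which case, treatment may be resumed at the next". The resumption it allows is one level down, after recovery.

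**The concern.** The two halves of the section differ on two points. The first is the reach of the waiver: unlimited in the text as worded, printed only for the first event in the table. The second is the counter: the text moves on when toxicity returns after a reduction has been made, whereas the table moves on with each occurrence, even if the first was waived and nothing was reduced.

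At stake are whether a treating physician keeps the dose, reduces it or stops the drug, and therefore the exposure delivered. Safety and tolerability are a secondary objective (section 2.2), section 13.1 requires treatment to stop when modifications lead to discontinuation, and section 14.0 tabulates adverse events requiring discontinuation separately. That tabulation would partly reflect which half of section 9.3.1 was followed.

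**Working it through.** The plan states no figure to reproduce here. The check is to trace both rules through every sequence of three drug-related grade 3 non-hematologic events.

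Notation: S = managed by routine supportive care; G = not so managed; same = hold, then resumption at the same dose allowed; R1, R2 = hold, then first or second reduction; remove* = removal by default, subject to footnote 2.

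Three readings are compared:

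1. *Text, literal*: the waiver is available at any event, and removal follows two reductions.
2. *Text, narrow*: the waiver is available only before any reduction, because the recurrence sentences do not repeat it.
3. *Table, broad*: the waiver applies at the first occurrence only, and the later grade 3 rows cover every grade 3 event.

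| Events | Text, literal | Text, narrow | Table, broad |
|---|---|---|---|
| SSS | same, same, same | same, same, same | same, R1, remove* |
| SSG | same, same, R1 | same, same, R1 | same, R1, remove* |
| SGS | same, R1, same | same, R1, R2 | same, R1, remove* |
| SGG | same, R1, R2 | same, R1, R2 | same, R1, remove* |
| GSS | R1, same, same | R1, R2, remove | R1, R2, remove* |
| GSG | R1, same, R2 | R1, R2, remove | R1, R2, remove* |
| GGS | R1, R2, same | R1, R2, remove | R1, R2, remove* |
| GGG | R1, R2, remove | R1, R2, remove | R1, R2, remove* |

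Default removal status after three events differs between table and literal text in 7 of 8 sequences (all but GGG). It differs between table and narrow text in 4 of 8 (every sequence starting with S). These are counts of rule conflicts; the sequences are not equally likely and the fractions are not patient rates.

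A narrow reading of the table is also possible, in which its later rows exclude manageable events. The table then gives no instruction for any sequence with S in second or third place, which is 6 of the 8. Two remain, GGG and SGG. GGG agrees with the text. SGG does not: the waived event sits in the table's own first-occurrence block, so the two G events are the second and third occurrences.

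Footnote 2 was then applied. In SGG, if investigator and sponsor agree, the patient resumes one level lower, which matches the text's second reduction. In SSS it cannot match the text: the table has already reduced once, and the footnote permits only a further step down.

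Other sections were checked for a tie-breaker. Section 9.2 caps reductions at three but does not say whether a waived event counts. Section 9.3.2 holds gastrointestinal toxicity until recovery and says nothing on resumption dose or counting. No section gives the text or the table precedence.

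**The case against.** The strongest reply is that Table 9-3 treats grade 3 toxicity and supportively manageable grade 3 toxicity as separate categories, so its later rows, which name only grade 3, concern events that were not waived. The text then fills the gap and three manageable events do not lead to removal. This reading is available, and because of it the three-event conflict cannot be called certain. It still leaves the table silent on repeats and does not resolve SGG, unless a waived event is held not to be an occurrence at all, which the table's layout contradicts.

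Other parts of the reply stand:

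- The second-reduction label in the table is only an example. Resuming one level lower works even if nothing was reduced before.
- The text is permissive. It does not oblige anyone to keep the dose, and its second reduction is optional.
- Removal in the table is a default, not absolute.
- This is a single-center trial, so the inconsistency would arise between treating physicians rather than between sites.

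A reader might also infer that patients removed before the first tumour assessment at 8 weeks become non-responders in the primary endpoint. The documents do not show this. Section 13.2.2 continues scheduled scans after discontinuation for reasons other than progression and a few listed exceptions, and section 14.0 replaces some patients who withdraw for reasons unrelated to disease before any response or progression. Three events, with a hold and recovery after each of the first two, would also have to fit within 8 weeks.

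Nor do the toxicity rates in section 3.2.8 size the problem. Drug-related grade 3/4 nausea (8%) and vomiting (5%), and grade 3/4 hypokalemia (5.1%), are pooled across 435 patients in all studies. The note to the grade 3/4 table says a patient with repeats of a term is counted once. Fatigue (23%) is not described anywhere as manageable by routine supportive care.

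**Conclusion.** The inconsistency is real and should be corrected. It is firmest for a waived first event followed by two non-manageable events: both rules give one reduction after the second event, and at the third the text gives a second reduction while the table gives default removal. That rests only on counting the waived event where the table places it, and footnote 2 can close the gap by agreement. For three supportively managed events, the literal text requires no reduction at any event. The table gives no reduction, then a reduction, then default removal if its later rows include manageable events; otherwise it does not address repeats. In this sequence the divergence begins at the second event, and the contrast between continuing and removal needs a third.

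The effect is on patient management, exposure and the tabulation of discontinuations. The documents give no frequency of repeat events, so the number of patients cannot be computed, and no effect on the primary endpoint is established.

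**What to change.** Reconcile the section 9.3.1 text and Table 9-3 so that both state the same rule on two points:

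- (a) whether the supportive-care waiver applies beyond the first occurrence;
- (b) whether a waived event counts toward removal, that is, whether the counter runs on occurrences or on reductions actually made.

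The table should show explicitly what follows when the first event was waived, and the example in its second-occurrence row should be worded to fit that case. Which rule applies is for the sponsor to decide. The cost is a protocol wording change and one revised table, with no added patients or procedures.

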### 9.3.2. Management of Gastrointestinal Toxicity

GI toxicities, such as anorexia, nausea, vomiting and diarrhea have been reported as probably related to mocetinostat. Associated conditions, including, but not limited to, dehydration, electrolyte abnormalities such as hypokalemia (sometimes with associated QTc prolongation), hypotension, and syncope have also been observed. Subjects experiencing GI toxicity should be closely monitored and treated as per guidelines mentioned below.

For anorexia, dehydration, nausea, vomiting, or diarrhea that is grade 3 or 4, or is prolonged grade 2 (more than 3 days), manage per institutional standard. Hold study treatment until resolution to grade 1 or better.

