### 9.2. Mocetinostat dose modification

Patients will be initiated at 70 mg mocetinostat three times per week for 1 cycle and observed for toxicities. If there are no grade 3 or higher drug related toxicities, the dose will be increased to 90 mg starting cycle 2 if thre are no grade 3 or higher treatment related toxicities.

Mocetinostat dose reduction will be administered at 20 mg below the current dose. For each patient, a maximum of 3 dose reduction (minimum dose of 35 mg three times per week) will be allowed after which the patient will be discontinued from treatment with mocetinostat (Table 9-2). Once a dose has been reduced during a treatment cycle, re-escalation will not be permitted during any subsequent cycle. If the administration of mocetinostat is interrupted for reasons other than toxicity, then treatment with the study drug may be resumed at the same dose. The same applies if the patient experienced an unacceptable toxicity not specifically described in Table 3-3 or Section 9.3, provided this toxicity resolved to  $\leq$  CTCAE grade 1, unless otherwise specified.

If treatment with the study drug is withheld for  $\geq$ 21 consecutive days, then study drug must be permanently discontinued. Patients who permanently discontinue the study drug should have followup for 30 days after discontinuation of all study treatment or resolution of the AE to  $\leq$  grade 1, whichever occurs first, that includes all study assessments appropriate to monitor the event.

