# 13.0 CRITERIA FOR REMOVAL FROM STUDY

### 13.1. Criterial for premature patient removal from study

Patients may voluntarily withdraw from the study or be removed from the study at the discretion of the investigator at any time. Patients may be withdrawn from the study if any of the following occur:

- Progressive disease
- Unacceptable toxicities
- Protocol deviation
- Lost to follow-up
- Pregnancy
- Discovery of patient ineligibility
- Errors in treatment compliance
- Administrative problems

In addition to the general study treatment withdrawal criteria, the following study specific criteria will also require premature study treatment discontinuation:

- Study treatment modifications that result in discontinuation
- Interruption of mocetinostat treatment for more than 21 days
- Use of prohibited medication
- Start of any other anti-neoplastic therapy

If a study treatment withdrawal occurs, or if the patient fails to return for visits, the investigator must determine the primary reason for a patient's premature withdrawal from study treatment and record this information in CRDB. In case of withdrawal from study treatment, the patient needs to indicate on the informed consent form whether she is willing to continue with subsequent follow-up procedures

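### Section 9.3.2 requires a hold for prolonged grade 2 GI toxicity, Table 9-3 makes a delay below grade 3 optional, and neither says which governs

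*Combined protocol and SAP*

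**What the plan says.** Section 9.3.2 tells the reader that "Subjects experiencing GI toxicity should be closely monitored and treated as per guidelines mentioned below". The guideline that follows names five GI events and sets two triggers. One is severity of grade 3 or 4. The other reads: "or is prolonged grade 2 (more than 3 days), manage per institutional standard. Hold study treatment until resolution to grade 1 or better". The second trigger is an instruction and leaves no discretion.

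Section 9.3.1 gives the general rule for drug-related non-hematologic toxicity and summarizes it in Table 9-3. In the row for toxicity below grade 3, listed under the first occurrence, the entry begins under the treatment-delay column: "May be implemented based on Investigator and subject" discretion, with the sponsor to be notified. Footnote 1 sends pericardial toxicity elsewhere. No footnote mentions GI toxicity.

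The prose of Section 9.3.1 is narrower than the table: "Dose reductions for lower-grade toxicities may also be implemented based on Investigator discretion; however the sponsor should be notified of such an event". It does not mention holds below grade 3.

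Section 9.2 applies to any withholding that reaches the limit: at "21 consecutive days, then study drug must be permanently discontinued". Section 13.1 sets the limit slightly differently ("Interruption of mocetinostat treatment for more than 21 days"). Section 9.3.1, in its grade 3 paragraph, allows an exception where the investigator, after discussion with the manufacturer, "deems that it is in the best interest of the subject to resume treatment".

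**The concern.** A patient with grade 2 nausea on day 4 meets the Section 9.3.2 trigger and also falls in the discretionary row of Table 9-3. A treating physician who keeps dosing follows the table and breaches the GI section. An auditor using one passage would record a deviation; an auditor using the other would not.

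What is at stake is consistent handling of a safety hold and the meaning of what is reported. Safety and tolerability is a secondary objective (Section 2.2), and Section 14.0 plans a separate tabulation of adverse events that lead to stopping the drug. Dose received, interruptions and some discontinuations would depend partly on which passage was followed.

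**Working it through.** The plan gives no figure for this point, so the check is a comparison of the passages, followed by a look at how many patients it could reach.

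**Side by side, for grade 2 GI toxicity lasting more than 3 days**

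| | Section 9.3.2 | Table 9-3, row below grade 3 |
|---|---|---|
| Scope | Five named GI events | All drug-related non-hematologic toxicity except pericardial |
| Hold | Required | Optional |
| Occurrence | Not limited | First occurrence only |
| Precedence over the other | Not stated | Not stated |
| Dose on resumption | Not stated | Not specified for this row |

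Holding satisfies both passages. Not holding satisfies only the table. The conflict is therefore confined to the decision to continue dosing.

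Section 9.3.2 gives no resumption dose, unlike the cystitis guidance in Section 9.3.3. A user must therefore return to Section 9.3.1 and Table 9-3, where the optional row applies.

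**Reach.** Section 3.2.8 gives drug-related rates from earlier mocetinostat trials (435 patients analyzed). Patients with worst grade 1 or 2 = any grade minus grade 3/4:

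| Event | Any grade | Grade 3/4 | Difference |
|---|---|---|---|
| Nausea | 66% | 8% | 58% |
| Diarrhea | 50% | not in the list of 5% or more, so below 5% | about 45% or more |
| Vomiting | 44% | 5% | 39% |
| Anorexia | 31% | 5% | 26% |

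Fatigue, at 63% the second commonest related event, is outside Section 9.3.2. Four of the five commonest drug-related events are therefore inside it.

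These differences mix grade 1, where neither passage requires a hold, with grade 2 of any duration. The documents give no grade 2 or duration split. If a share s of the nausea group had grade 2 beyond 3 days, the affected proportion would be 58% × s. Purely as assumptions:

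- s = 10%: 5.8%, or 0.058 × 56 = 3.2 of the 56 planned patients
- s = 25%: 14.5%, or 8.1 patients
- s = 50%: 29%, or 16.2 patients

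The width of this range shows that the documents do not determine the number.

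**Route to a permanent stop.** A hold under Section 9.3.2 ends at grade 1 or better. Under Section 9.2 the drug is stopped only if the withholding lasts 21 consecutive days or more. That limit covers any withholding, required or optional, and has no GI exclusion.

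**The case against.** The strongest reply is that Section 9.3 runs from general to specific. Section 9.3.1 is the default, and the GI, cystitis and pericardial sections follow with their own rules. Section 9.3.2 directs that GI events be treated by its own guideline, and a physician who holds complies with everything. Cystitis also has its own hold rule in Section 9.3.3 and is also absent from footnote 1, so the footnote is not a full list of special rules. On this view only a pointer is missing.

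That reading is plausible, and it limits the size of the point. It does not remove it. No precedence is stated, and footnote 1 is a poor guide to intent: it cites a Section 6.2.2, whereas pericardial management is in Section 9.3.4. As printed, the table grants a discretion over a safety hold that Section 9.3.2 denies.

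A second reply is that the discretion may concern dose reduction only, as the Section 9.3.1 prose says. The table entry, however, starts under treatment delay. Whether it fills that column alone or spans both, it reaches delays. The row is limited to first occurrence, so a reader who infers that every toxicity below grade 3 is left to discretion goes beyond the text.

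A third reply is that this is a single-center, single-arm trial, so no difference between sites or arms can arise. That stands. Differences between patients and treating physicians remain possible.

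**Conclusion.** The point holds as an unreconciled instruction. For prolonged grade 2 nausea, vomiting, diarrhea, anorexia or dehydration, continued dosing is either allowed or a deviation, depending on the passage read. It can affect exposure, tolerability summaries and the discontinuation table. Its frequency cannot be derived. The 58% for nausea describes earlier patients whose related nausea never exceeded grade 2. They came from 13 trials with mixed diseases and doses, some with combination therapy, and only an unknown part of them would meet the trigger.

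Three stronger readings are tempting, and the documents do not support them:

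- **That prolonged grade 2 GI toxicity leads to permanent discontinuation.** This needs a hold that reaches the 21-day limit. No frequency is given for that, and the limit applies equally to a discretionary hold.
- **That the primary response rate is distorted.** Section 14.0 replaces some withdrawals unrelated to disease, so a stop before any response could affect who is counted among the 25 analyzable patients per subtype. Nothing in the documents shows that this would happen or in which direction.
- **That the conflict covers all the commonest toxicities.** Fatigue is not in Section 9.3.2.

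**What to change.** Reconcile Section 9.3.2 with Section 9.3.1 and Table 9-3. Add a footnote to the row below grade 3 saying which passage governs prolonged grade 2 GI toxicity, and a matching sentence in Section 9.3.2.

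The same edit should settle the grade 3/4 GI instructions. For grade 4, Section 9.3.2 says hold until grade 1 or better. Table 9-3 removes the patient from therapy, and the Section 9.3.1 prose discontinues unless investigator and sponsor agree otherwise. For grade 3, Section 9.3.2 is silent on the dose at resumption, which Table 9-3 addresses. The Section 6.2.2 reference in footnote 1 can be corrected at the same time.

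Which clinical rule applies is for the investigators and sponsor to decide. The cost is a footnote and a sentence or two, with no extra visits, patients or analyses.

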### 9.3.3. Management of Mocetinostat associated Cystitis

In the event of a subject experiencing symptoms of cystitis (dysuria, pollakiuria, hematuria, urgency or bladder spasm) suspected to be mocetinostat related:

- Encourage adequate hydration.
- Conduct urinalysis, urine culture, blood urea nitrogen (BUN), creatinine and complete blood count (CBC).
- If clinically significant symptoms persist despite a negative work-up or treatment of an associated condition, hold study drug until resolution of clinically significant symptoms.
- Resume dosing of mocetinostat when medically appropriate at the same or a reduced dose level as per the Investigator's judgment.

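### Section 9.3.3 permits the same dose after drug-related cystitis of any grade, and no text says that the stricter rules in 9.3.1 and Table 9-3 prevail

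*Combined protocol and SAP*

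**What the plan says.** Section 9.3.3 applies to cystitis symptoms suspected to be due to the drug. After hydration and a work-up it gives a symptom-based hold: "If clinically significant symptoms persist despite a negative work-up or treatment of an associated condition, hold study drug until resolution of clinically significant symptoms". It then says "Resume dosing of mocetinostat when medically appropriate at the same or a reduced dose level", and leaves the choice to the investigator. No CTCAE grade, occurrence count or sponsor agreement appears.

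Section 9.3.1 and Table 9-3 govern drug-related non-hematologic toxicity by grade:

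- **Grade 3.** Hold until recovery to grade 1 or baseline, then go down one dose level. The text makes an exception: "If the toxicity can be managed by routine supportive care, such as anti-emetics or electrolyte supplementation, then a dose reduction is not required". Table 9-3 lists that exception only under the first occurrence.
- **Second grade 3.** Table 9-3 gives the next lower level. The 9.3.1 text says that a second reduction may be made.
- **Third grade 3.** "However if grade 3 non-hematologic toxicity again recurs, then the subject should be removed from protocol therapy". Footnote 2 of Table 9-3 lets investigator and sponsor agree on benefit, and then "treatment may be resumed at the next lower dose level as described above following recovery".
- **Grade 4.** "Subjects who experience grade 4 non-hematologic toxicities should have study treatment discontinued", again with an exception by investigator-sponsor agreement, at a lower dose.

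Footnote 1 of Table 9-3 sends only pericardial toxicity to another section.

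**The concern.** Cystitis is a non-hematologic toxicity, so it falls within Table 9-3, yet 9.3.3 ends with its own dosing instruction and that instruction is looser. An investigator who opens 9.3.3 and acts on it could resume the same dose after grade 4 cystitis, or after repeated grade 3 cystitis, without the reduction or the sponsor agreement that the general rule calls for.

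What is at stake is patient safety for a known toxicity. Section 3.2.8 reports bladder toxicity with this drug, rarely including hemorrhagic cystitis, and its cystitis paragraph says that symptoms mostly follow several cycles. Dosing rises to 90 mg from cycle 2 if no grade 3 or higher related toxicity has occurred, so cystitis would tend to appear after escalation.

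**Working it through.** The plan states no figure on this point, so the check sets the rules side by side.

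**Resumption dose by case**

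| Cystitis, drug related | 9.3.3 allows | 9.3.1 and Table 9-3 | Do they differ? |
|---|---|---|---|
| Below grade 3 | Same or lower | Delay or reduction is discretionary | No |
| First grade 3, controlled by supportive care | Same or lower | Hold; no reduction needed | No |
| First grade 3, not controlled | Same or lower | Next lower level | Yes |
| Second grade 3 | Same or lower | Next lower level (table) | Yes, against the table |
| Third grade 3 | Same or lower | Removal, or next lower level if investigator and sponsor agree | Yes |
| Grade 4 | Same or lower | Removal, or a lower level if investigator and sponsor agree | Yes |

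**Does another section settle it?**

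- Section 9.2 lets dosing resume unchanged after some toxicities, but only those not described in Table 3-3 or Section 9.3. Cystitis is described in 9.3.3, so the clause does not reach it.
- The hold in 9.3.3 is an extra trigger. It does not cancel the grade 3 hold in Table 9-3, so the holds do not conflict.
- Sections 9.2 and 13.1 limit interruptions to about 21 days, and 9.3.1 lets the investigator, in discussion with the company, depart from that limit. Serious events go to the IRB and the company within 5 calendar days (11.2.1). Neither provision sets the dose on resumption.

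**Size for an affected patient**

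The alternative to the same dose is one step down. The first step uses the 20 mg rule in 9.2, and the others use Table 9-2:

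- 90 to 70 mg: (90 − 70)/90 = 22%
- 70 to 50 mg: (70 − 50)/70 = 29%
- 50 to 35 mg: (50 − 35)/50 = 30%

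At 35 mg no lower level exists. There, and after grade 4 or a third grade 3 without agreed benefit, the alternative is stopping.

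**How many patients**

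The documents give no count of grade 3 or 4 cystitis. A loose ceiling comes from Section 3.2.8, which lists related grade 3/4 terms at 5% or more of 435 patients and names no bladder term.

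- Exact cut-off: 0.05 × 435 = 21.75, so at most 21 patients per term.
- If percentages were rounded, 20/435 = 4.6% would print as 5%, so at most 19. The grade 3/4 table suggests rounding, because it prints terms at 4.6% and 4.8%.

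Assume that this pooled rate carries over. If both cohorts stop at 10 patients, the ceiling is below 0.05 × 20 = 1.0 patient per term (20 × 19/435 = 0.9 with rounding). At full enrolment of 56 it is below 0.05 × 56 = 2.8 (56 × 19/435 = 2.4). These are ceilings on all grade 3/4 events of one term, not estimates of dose discrepancies. They do not cover all bladder terms together, and the pooled data mix tumours, doses and combinations.

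**The case against.** The strongest reply is that nothing here is contradictory. Section 9.3.3 is permissive: it allows the same or a reduced dose when medically appropriate. An investigator who reduces or stops as Table 9-3 directs breaches neither section. The structure also favours Table 9-3. Only pericardial toxicity is sent elsewhere, and the footnote to Table 9-2 ties reductions to the worst preceding toxicity. Section 9.3.2 sets a hold for gastrointestinal toxicity but no resumption dose, so it relies on the general rule.

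Most of this stands. A reader might infer that the protocol contradicts itself outright, or that it directs same-dose treatment after grade 4 cystitis. The documents support neither, because 9.3.3 permits the same dose and does not require it. What remains is that the precedence of Table 9-3 is an inference. Section 9.3.2 names grades and leaves the dose to the general rule; 9.3.3 names no grade and supplies its own dose rule. The opposite inference, that the specific section overrides the general one, is equally unstated.

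A reader might also infer that every grade 3 cystitis is affected. It is not: a first grade 3 controlled by supportive care may keep its dose under both sections. That concession does not extend to repeat grade 3 under Table 9-3. The 9.3.1 text does not tie the supportive-care exception to an occurrence, so the second-occurrence difference rests on the table.

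**Conclusion.** This is a low-impact inconsistency between safety rules. Following the stricter rule satisfies both sections, but no text says that it prevails, and 9.3.3 read alone allows a less safe dose in four cases: first grade 3 not controlled by supportive care, second grade 3, third grade 3, and grade 4.

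Few patients, possibly none, would be affected. The documents support only a qualitative statement that bladder toxicity was seen in a few patients; the ceilings rest on the pooled rate carrying over. Section 9.3.1 words its rules as recommendations, while Table 9-3 states them flatly, so the discrepancy is clearest against the table. The response endpoint, the Simon decision rule and its error rates are untouched. The wording is still worth correcting, because the toxicity is known and the change costs almost nothing.

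**What to change.** State two things in 9.3.3:

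1. Same-dose resumption at the investigator's judgement applies only to cystitis below grade 3, or to a first occurrence of grade 3 that supportive care controls, after recovery to grade 1 or baseline.
2. All other grade 3 cystitis, including any second or third occurrence, and all grade 4 cystitis follow 9.3.1 and Table 9-3, including the investigator-sponsor exceptions.

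The words on first occurrence matter. Without them the amendment would allow the same dose after repeat grade 3 cystitis, against the second- and third-occurrence rows of Table 9-3.

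The cost is one or two sentences of protocol wording, and slightly less investigator discretion for severe or recurrent cystitis. The sample size and the analysis do not change.
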